9.5.3 Analyses of Exploratory Endpoints

In subjects who completed the EBBINGHAUS study (Study 20130385), descriptive statistics for the exploratory endpoints (raw score and change from baseline of SWM strategy index of executive function, SWM between-errors score, PAL total errors adjusted and RTI median 5-choice reaction time) will be provided by each scheduled visit for OLE CANTAB analysis set.

The change and percent change from baseline in lipid parameters at each scheduled visit will be summarized based on the OLE Safety Analysis Set for the **combined parent and OLE study periods.** For continuous exploratory endpoints, summary statistics (number of subjects, mean, median, standard deviation or standard error, first and third quartiles, minimum, and maximum) at all scheduled visits will be calculated. Subject incidence, exposure-adjusted subject incidence rate, and yearly Kaplan Meier (K-M) estimates of positively reviewed events (by an independent external CEC) will be summarized **for both the OLE only study period and combined parent and OLE study periods.** All deaths will be summarized by cardiovascular death (including coronary heart disease death), non-cardiovascular death and undetermined cause of death.

9.6 Safety Analyses

9.6.1 Safety Analysis of Low LDL-C

The safety analyses (TEAE and serious TEAE) will be summarized for subjects with any postbaseline LDL-C and all postbaseline LDL-C with the cutoffs of < 25 mg/dL, < 40 mg/dL and ≥ 40 mg/dL for the OLE **only** study period using the OLE safety analysis set.

In addition, the safety analyses will be summarized in subjects with 2 consecutive postbaseline LDL-C < 25 mg/dL and LDL-C < 40 mg/dL separated by at least 21 days.

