To decrease the morbidity and mortality associated with CVD, over 50 million patients in the United States (US), Europe, and Japan are currently treated with dyslipidemia therapies. The rationale for treatment of dyslipidemia, particularly elevated LDL-C, extends from extensive clinical study data in both primary and secondary prevention that demonstrates the reduction in total cholesterol, non-HDL-C, and most importantly, LDL-C through pharmacological therapies, particularly statins, lowers the risk of CVD events ([Kannel, 1995](#); [Kannel et al, 1979](#); [Kannel et al, 1974](#)). The most recent [Cholesterol Treatment Trialists' Collaboration \(2010\)](#) meta-analysis which included 21 randomized controlled studies of statin versus control involving nearly 170,000 patients showed that for every approximately 1 mmol/L reduction of LDL-C, there was an approximately 20% reduction in the risk of major vascular events (coronary death, nonfatal myocardial infarction [MI], coronary revascularization, or stroke). Importantly, this meta-analysis, which also evaluated 5 studies that compared more versus less intensive statin therapy, did not find an LDL-C threshold for risk reduction; additional vascular risk reduction is possible in patients with low LDL-C. The opportunity for further cardiovascular risk reduction is also consistently seen in the numerous

primary and secondary prevention studies where subjects were treated with statins to their LDL-C goal, the results of which have manifested in durable, dramatic changes in medical practice and have consequently saved millions of lives.

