9. SAFETY DATA COLLECTION, RECORDING, AND REPORTING

9.1 Definition of Safety Events

9.1.1 Disease-related Events

Disease-related events are events (serious or nonserious) anticipated to occur in the study population due to the underlying disease. **All serious disease-related events will be recorded and reported to the sponsor or designee within 24 hours.** In this study, subjects have hyperlipidemia and clinically evident atherosclerotic CVD.

Therefore, disease-related events include the following: manifestations and complications of atherosclerotic vascular disease such as coronary artery disease, angina, myocardial infarction, ischemic stroke, TIA, carotid artery disease, peripheral vascular disease (including complications such as claudication), and testing suggesting progression of atherosclerotic vascular disease. Such events do not meet the definition of an adverse event unless assessed to be more severe than expected for the subject's condition.

Disease-related events and/or disease-related outcomes that do not qualify as serious adverse events include:

- An event which is part of the normal course of disease under study (eg, disease progression in oncology or hospitalization due to disease progression) is to be reported as a disease-related event.
- Death due to the disease under study is to be recorded on the Event eCRF.

If the outcome of the underlying disease is worse than that which would normally be expected for the subject, or if the investigator believes there is a causal relationship between the investigational product (evolocumab)/protocol required-therapies and disease worsening, this must be reported as an adverse event or serious adverse event.

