5.3 Other Study Related Definitions

Treatment-Emergent Adverse Event (TEAE)

Events are categorized as Adverse Events (AEs) or **Disease-related Events (DREs)** starting on or after first dose of investigational product as determined by the flag indicating if the event started prior to the first dose on the Events eCRF and up to the EOS/Safety Follow-up visit or 30 days after the last administration of evolocumab, whichever is earlier.

Treatment-Emergent Disease-Related Events

Events categorized as Disease-related Events defined in Protocol Section 9.1.1 starting on or after first dose of investigational product as determined by the flag indicating if the disease-related event started prior to the first dose on the Events eCRF and up to the EOS/Safety Follow-up visit or 30 days after the last administration of evolocumab, whichever is earlier.

Analytical Study Week Assignments

Analytical windows will be used to assign parameters to study weeks. The algorithm is provided in Appendix A.

Investigational Product (IP)

Investigational product includes evolocumab 140 mg every two weeks (Q2W) and 420 mg monthly (QM).

IP Exposure Period in Months (For OLE period)

For subjects whose last IP dose is Q2W:

IP exposure period in OLE period= $[\min(\text{last IP dose date in OLE period} + 14 \text{ days, EOS date}) - \text{first IP dose date in OLE period} + 1] / 365.25 \times 12$

For subjects whose last IP dose is QM:

IP exposure period in OLE period= $[\min(\text{last IP dose date in OLE period} + 28 \text{ days, EOS date}) - \text{first IP dose date in OLE period} + 1] / 365.25 \times 12$

IP Exposure Period in Months (For combined the parent and OLE periods)

For subjects whose last IP dose is Q2W:

IP exposure period in combined periods= $[\min(\text{last IP dose date in OLE period} + 14 \text{ days, EOS date in OLE period}) - \text{first IP dose date in the parent period} + 1] / 365.25 \times 12$

For subjects whose last IP dose is QM:

IP exposure period in combined periods= $[\min(\text{last IP dose date in OLE period} + 28 \text{ days, EOS date in OLE period}) - \text{first IP dose date in the parent period} + 1] / 365.25 \times 12$

Study Exposure Period in Months (For OLE period)

For each subject, study exposure period in OLE period = $[(\text{EOS date} - \text{enrollment date}) + 1] / 365.25 \times 12$

Study Exposure Period in Months (For combined the parent and OLE periods)

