9.5.1 Analyses of Primary Endpoint

The current Medical Dictionary for Regulatory Activities version at the time of data lock will be used to code all adverse events (AEs) and disease related events to a system organ class and a preferred term.

Treatment-emergent adverse events are defined in [Section 5.3](#).

The subject incidence and exposure-adjusted subject incidence rate of all treatment-emergent adverse events, serious adverse events, fatal adverse events, adverse events leading to withdrawal of evolocumab, device-related adverse events, and disease-related events will be tabulated by system organ class (SOC), high level term (HLT), and preferred term (PT) in alphabetical order for the OLE only study period using the OLE safety analysis set. These events will also be presented by yearly subject exposure time intervals. All adverse event summaries for the primary analysis of the primary endpoint will include all treatment-emergent events reported on the Event eCRF, including CEC reviewed events and disease related events.

The analyses described above (subject incidence, exposure-adjusted subject incidence rate) will also be performed combining data from the OLE study and the parent study using the OLE safety analysis set and also be analyzed separately for the subgroup of subjects who were randomized to and received evolocumab group in the parent study with ≥ 7 years of the combined exposure for evolocumab across the **combined** parent and OLE **study**. Events from parent study classified as Target IP TEAEs will be included (adverse events occurring from the first dose of IP date to 30 days after the last dose of IP date or EOS, whichever occurs first). Disease-related events from the OLE study will be reclassified as adverse events and positively reviewed events from the OLE

study will not be included to remain consistent with parent study adverse event reporting. This analysis will be presented by the randomized treatment in the parent study.

Subject incidence of treatment emergent and serious adverse events occurring in at least 1% of the subjects by preferred term will be provided in descending order of frequency for the OLE **only** study period **and combined parent and OLE study periods.**

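### The low-LDL-C safety tables (SAP 9.6.1) count atherosclerotic disease-related events in the same totals as other adverse events, which can dilute, and in some scenarios offset, an excess of other events at low LDL-C

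*SAP*

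**What the plan says.** SAP 9.6.1 is the only planned safety analysis by achieved LDL-C; the LDL-C subgroup in SAP 4.2 is by baseline value. It states that "The safety analyses (TEAE and serious TEAE) will be summarized for subjects with any postbaseline LDL-C and all postbaseline LDL-C". The groups are formed by cutting at 25 and 40 mg/dL, and the analysis covers the OLE period only. A further summary is planned for subjects with two consecutive low values. The section names no row with DREs removed and no row with DREs alone.

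The term TEAE comes from SAP 5.3: "Events are categorized as Adverse Events (AEs) or Disease-related Events (DREs) starting on or after first dose". The same section also defines treatment-emergent DREs separately.

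Protocol 9.1.1 describes DREs as "manifestations and complications of atherosclerotic vascular disease such as coronary artery disease, angina, myocardial infarction, ischemic stroke, TIA, carotid artery disease" and similar conditions, and says: "Such events do not meet the definition of an adverse event unless assessed to be more severe than expected for the subject's condition". Protocol 2.1 cites a statin meta-analysis in which, for each reduction of about 1 mmol/L in LDL-C, "there was an approximately 20% reduction in the risk of major vascular events".

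SAP 9.5.1 says the adverse event summaries for the primary analysis "will include all treatment-emergent events reported on the Event eCRF, including CEC reviewed events and disease related events". It also lists DREs as a category of their own, but not by LDL-C group. It removes positively CEC-reviewed events only in the combined parent and OLE analysis.

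**The concern.** The effect of holding LDL-C below 40 mg/dL is a secondary objective (protocol 1.2) and part of the study's rationale (protocol 2.3). SAP 9.6.1 is where a reader will look for harm at low LDL-C. If the total in each LDL-C group includes events that low LDL-C is expected to prevent, a fall in those events works against any rise in the others. The analysis is descriptive, with no model behind it, so the displayed totals carry the message. A modest excess of non-atherosclerotic events could look smaller than it is, or absent.

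**Working it through.** **The plan's own figure.** The only design calculation is the table of confidence interval widths (protocol Table 2, SAP Table 3-1). It reproduces as 2 × 1.96 × √(p(1−p)/5000): for p = 5% this gives 1.208%, as stated. All eight rows agree once the half-width is rounded to three decimals and doubled. The present point does not depend on it.

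**Inputs**
- From protocol 2.1: vascular risk ratio (RR) about 0.80 per 1 mmol/L.
- Assumed: DREs are a share s of 30%, 40% or 50% of serious TEAEs in the higher-LDL-C group. The documents give no figure.
- Assumed: the mean LDL-C contrast between groups is 15 mg/dL or 1 mmol/L. At 38.67 mg/dL per mmol/L, 15 mg/dL is 0.39 mmol/L.
- Assumed: the statin-trial risk ratio applies to DREs and to groups formed by achieved LDL-C, and serious DREs are counted as serious TEAEs.

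**Step 1: vascular risk ratio.** At 1 mmol/L it is 0.80. At 15 mg/dL it is 0.8^0.39 = 0.917.

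**Step 2: total with no effect on other events.** Ratio = s × RR + (1 − s). At 1 mmol/L this is 0.94, 0.92 and 0.90 for s = 30%, 40% and 50%. At 15 mg/dL and s = 30% it is 0.3 × 0.917 + 0.7 = 0.975.

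**Step 3: excess in other events that leaves the total unchanged.** Solve s × RR + (1 − s)(1 + x) = 1, giving x = s(1 − RR)/(1 − s).

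| Contrast | s = 30% | s = 40% | s = 50% |
|---|---|---|---|
| 15 mg/dL (RR 0.917) | 3.6% | 5.5% | 8.3% |
| 1 mmol/L (RR 0.80) | 8.6% | 13.3% | 20.0% |

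**Step 4: check on the subject-incidence scale.** Steps 2 and 3 treat events as additive, whereas the SAP reports subjects with at least one event. Assuming independence, the risk of any serious event is 1 − (1 − p_other)(1 − p_DRE).
- Assume a 40 mg/dL contrast (RR 0.794), with serious DRE risk 15% and other serious risk 25% in the higher group, and a true ratio of 1.10 for other events.
- Higher group: 1 − 0.75 × 0.85 = 36.25%.
- Lower group: 1 − 0.725 × (1 − 0.15 × 0.794) = 36.1%.
- The combined row shows a ratio of 0.997. With DREs separated it shows 27.5% against 25.0%, a ratio of 1.10.
- With a 15 mg/dL contrast and serious DRE risk 5%, other inputs unchanged, the same true 1.10 appears as 1.072, so it is diluted and still visible.

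Over a wider assumed grid (serious DRE risk 5% to 20%, other serious risk 20% to 35%, contrast 15 to 60 mg/dL), a true ratio of 1.10 appears as anything from 0.918 to 1.080. The ratio that is exactly cancelled runs from 1.008 to 1.273.

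**The case against.** **The serious row may not contain DREs.** Protocol 9.1.3 excludes DREs from serious adverse events unless they are worse than typical or thought to be caused by treatment. The SAP change log explains the term serious TEAE in 9.6.1 as limiting the summary to serious adverse events that are treatment-emergent. Table 9-1 lists serious adverse events and DREs separately. Against this, SAP 5.3 read literally includes DREs, and protocol 9.1.1 recognises serious DREs. The point stands as an ambiguity, and the arithmetic above applies only if serious DREs are counted.

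**Only some rows are affected.** SAP 9.6.1 does not say whether its tables go down to system organ class or preferred term. If they follow the layout in SAP 9.5.1, an excess in classes without atherosclerotic terms stays visible. This stands: masking is confined to top-line totals and to classes that contain vascular terms.

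**The size is assumed.** The 30% to 50% share has no source in the documents. The under-25 group is nested in the under-40 group, and under the any-value grouping one subject can be both below and above 40 mg/dL, which narrows the contrast. The 20% figure is for major vascular events on statins, while DREs also cover angina, claudication and test findings. Achieved LDL-C groups also differ in adherence, statin intensity and baseline risk. All of this stands, and is why a range is given.

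**Counting all events is deliberate.** Protocol 10.4.2 specifies it for the primary summaries, so a reader should not infer that including DREs there is an error. The case here is only for an added split in SAP 9.6.1.

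**Conclusion.** The point holds as a limited one. As SAP 5.3 and 9.6.1 are written, the any-TEAE total by achieved LDL-C includes events that low LDL-C is expected to reduce, and the any-serious-TEAE total may do so. Under the stated assumptions the fully masked relative excess in other serious events is about 4% to 20%. With few DREs or a small LDL-C contrast, an excess is diluted, not erased. No figure is offered for the any-TEAE row, because the DRE share there is unknown.

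A reader might infer that these tables will cancel a real harm signal, or that low LDL-C is bound to look protective. The documents do not support that: full cancellation needs particular combinations of assumed rates and contrasts, term-level tables may show the excess anyway, and confounding between non-randomized groups could move the DRE contrast in either direction. This is a cheap improvement, not the correction of an invalid analysis.

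**What to change.** In SAP 9.6.1, state whether serious TEAEs include serious DREs. Then for each LDL-C group, including the groups with two consecutive low values, tabulate:

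- (a) TEAEs and serious TEAEs excluding events categorized as DREs on the Event eCRF;
- (b) treatment-emergent DREs as already defined in SAP 5.3;
- (c) the current all-event total.

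Do not build (a) by borrowing the SAP 9.5.1 rule that drops positively CEC-reviewed events. Those include all deaths and all strokes (protocol 10.1.1.3), so the rule would take non-cardiovascular deaths and non-ischemic strokes out of the block meant to show harm. Non-cardiovascular and undetermined deaths, non-ischemic stroke and other non-atherosclerotic events should stay in (a).

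The cost is a few sentences in the SAP and one or two extra blocks per table. The event category is already collected, so no new data are needed.

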3. EXPERIMENTAL PLAN

3.1 Study Design

This is a multicenter, open-label extension study designed to assess the long-term safety of evolocumab in subjects who completed the FOURIER study, a randomized placebo-controlled study of evolocumab in subjects with clinically evident atherosclerotic CVD on stable effective statin therapy. Eligible subjects at sites participating in FOURIER OLE who have signed the FOURIER OLE informed consent may be enrolled at the completion of FOURIER. Enrollment of eligible subjects may be limited at the site level to maintain a 1:1 ratio between the following subject populations:

- subjects with \geq 2 years of study exposure in FOURIER and
- subjects who have less than 2 years of study exposure in FOURIER and did not participate in EBBINGHAUS

In this study, laboratory assessments will be performed at week 12 and thereafter approximately every 24 weeks from day 1 (see [Section 7.2](#)); the corresponding blood samples will be processed using a central laboratory. To preserve the integrity of FOURIER blinding, no local lipid assessments may be performed until either FOURIER is unblinded or at least 12 weeks after a subject's last administration of FOURIER investigational product (evolocumab or placebo), whichever is first. Upon enrollment in this study (FOURIER OLE), subjects will receive evolocumab 140 mg every 2 weeks (Q2W) or 420 mg monthly (QM), according to their preference. Frequency and corresponding dose of administration can be changed at any scheduled time point where evolocumab is supplied to the subject, provided the appropriate supply is available. It is recommended that subjects continue the same background LLT, including statin, as taken during FOURIER. This study will continue for 260 weeks (approximately 5 years). Subjects ending administration of evolocumab should continue study assessments until the end of study (EOS).

All subjects will be followed and complete procedures/assessments from enrollment through the date of study termination unless the subject has withdrawn consent, irrespective of whether the subject is continuing to receive treatment. All deaths and cardiovascular events of interest (MI, stroke, coronary revascularization, hospitalization for unstable angina, hospitalization for heart failure, and transient ischemic attack [TIA]) will be reviewed by an independent external Clinical Events Committee (CEC), using standardized definitions.

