4. SUBJECT ELIGIBILITY

4.1 Inclusion and Exclusion Criteria

4.1.1 Inclusion Criteria

- 101 Subject has provided informed consent before initiation of any study-specific activities/procedures.
- 102 Subject has completed FOURIER (Study 20110118) while still receiving assigned investigational product.

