4.1.2 Exclusion Criteria

- 201 Investigational product was permanently discontinued during FOURIER for any reason, including an adverse event or serious adverse event.
- 202 Subject is currently receiving treatment in another investigational device or drug study, or ended treatment on another investigational device or drug study(ies) within less than 4 weeks. Other investigational procedures while participating in this study are excluded.
- 203 Subject is not likely to be available to complete protocol-required study visits or procedures and/or to comply with required study procedures to the best of the subject's and investigator's knowledge.

204 Subject has a history or evidence of any other clinically significant disorder, condition, or disease that, in the opinion of the investigator or Amgen physician, if consulted, would pose a risk to subject safety or interfere with the study evaluation, procedures, or completion.

205 Subject has a known sensitivity to any of the active substances or excipients (eg, sodium acetate) to be administered during dosing.

206 Female subject is pregnant or breastfeeding or is planning to become pregnant or planning to breastfeed during treatment with evolocumab and within 15 weeks after the end of treatment with evolocumab.

207 Female subjects of childbearing potential who are not willing to use an acceptable method(s) of effective birth control during treatment with evolocumab and for an additional 15 weeks after the end of treatment with evolocumab are excluded.

Female subjects of non-childbearing potential are not required to use contraception during the study and include those who have had a hysterectomy, bilateral salpingectomy, bilateral oophorectomy, or who are postmenopausal. Postmenopausal is defined as 12 months of spontaneous and continuous amenorrhea in a woman \geq 55 years old; or age $<$ 55 years but no spontaneous menses for at least 2 years; or age $<$ 55 years and spontaneous menses within the past 1 year, but currently amenorrheic (eg, spontaneous or secondary to hysterectomy), and with postmenopausal gonadotropin levels (luteinizing hormone and follicle-stimulating hormone [FSH] levels $>$ 40 IU/L), postmenopausal estradiol levels ($<$ 5 ng/dL), or according to the definition of postmenopausal range for the laboratory involved.

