7.2.2 Treatment

The following procedures will be completed during the 5-year (260-week) treatment period at the times designated in the schedule of assessments ([Table 1](#)). If administered at the site, evolocumab is to be administered after completion of the blood draws and vital signs.

- review of targeted concomitant therapy
- review of adverse events, serious adverse events, device-related adverse effects, and disease-related events
- vital signs (sitting blood pressure and heart rate)
- body weight
- **coronary revascularization procedure and death information (sites will be prompted for this information when necessary)**
- CANTAB SWM, PAL, and RTI tests (subjects who participated in the EBBINGHAUS study only)

Approved

- blood draws for fasting lipids (\geq 9-hour fasting sample), ApoA1, ApoB, and Lp(a)
- blood draw or urine sample for a serum or urine pregnancy test (women of childbearing potential only)
- administration of evolocumab at study site (see [Section 6.2.1](#) for instruction and supervision of subjects), if applicable
- reconciliation of used evolocumab, and dispensing evolocumab (prefilled AI/Pens or PIs), if applicable

The investigator should instruct the subject to report to the site (eg, by telephone call) any adverse events, device-related adverse effects, serious adverse events, or disease-related events at any time (ie, between scheduled visits). In addition, subjects will be contacted by telephone as designated in the schedule of assessments ([Table 1](#)) for collection of adverse events, device-related adverse effects, serious adverse events, or disease-related events.

In addition to the time points listed in the schedule of assessments ([Table 1](#)), all CANTAB assessments should be performed if a subject from the EBBINGHAUS study reports a neurocognitive adverse event.

If, in the opinion of the investigator, a subject is unable to tolerate evolocumab, that subject will discontinue evolocumab but will continue to return for all other study procedures and measurements until the EOS.

If a subject withdraws from the study early, investigators should make every effort to complete and report the observations as thoroughly as possible up to the date of withdrawal. If possible, the end of investigational product administration procedures should be completed at the time of withdrawal.

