8. WITHDRAWAL FROM TREATMENT, PROCEDURES, AND STUDY

8.1 Subjects' Decision to Withdraw

Subjects have the right to withdraw from the study at any time and for any reason without prejudice to their future medical care by the physician or at the institution.

Subjects can decline to continue receiving evolocumab and/or other protocol-required therapies or procedures at any time during the study but continue participation in the study. If this occurs, the investigator is to discuss with the subject the appropriate processes for discontinuation from evolocumab or other protocol-required therapies and must discuss with the subject the possibilities for continuation of the schedule of assessments (Table 1) and collection of data, including endpoints and adverse events and must document this decision in the subject's medical records. The investigator must discuss the different options of follow-up (eg, in person, by telephone/mail, through family/friends, in correspondence/communication with other treating physicians, from review of the medical records or public records as permitted by applicable law). Such public record searches may be conducted by the site or vendors approved by the site. Subjects who have discontinued evolocumab and/or other protocol-required therapies or procedures should not be automatically removed from the study. Whenever safe and feasible, it is imperative that subjects remain on-study to ensure safety surveillance and/or collection of outcome data.

Withdrawal of consent for a study means that the subject does not wish to receive further protocol-required therapies or procedures, and the subject does not wish to or is unable to continue further study participation. Subject data up to withdrawal of consent will be included in the analysis of the study, and where permitted, publically available data can be included after withdrawal of consent. The investigator is to discuss with the subject appropriate procedures for withdrawal from the study.

Approved

8.2 Investigator or Sponsor Decision to Withdraw or Terminate Subjects' Participation Prior to Study Completion

The investigator and/or sponsor can decide to withdraw a subject(s) from evolocumab and/or other protocol-required therapies, protocol procedures, or the study as a whole at any time prior to study completion.

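### SAP 9.6.1: membership of the 'all postbaseline LDL-C' groups depends on samples taken after treatment-ending AEs and on length of follow-up, so these groups are not comparisons by LDL-C level

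*SAP*

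**What the plan says.** SAP 9.6.1 tabulates TEAEs and serious TEAEs by LDL-C reached on study. They "will be summarized for subjects with any postbaseline LDL-C and all postbaseline LDL-C with the cutoffs of" <25, <40 and ≥40 mg/dL, for the OLE-only period in the OLE safety analysis set. A further summary is made "in subjects with 2 consecutive postbaseline LDL-C < 25 mg/dL and LDL-C < 40 mg/dL separated by at least 21 days".

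Four other provisions decide what goes into these groups:

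- **Baseline.** SAP 5.1 takes it from the parent study, so every OLE value is postbaseline.
- **Sampling after stopping.** Protocol 3.1 and SAP 3.1 keep subjects in assessments after they stop evolocumab. Under Protocol 7.2.2, a subject who cannot tolerate the drug "will discontinue evolocumab but will continue to return for all other study procedures and measurements until the EOS". SAP Appendix A runs the last lipid window to EOS.
- **Event counting.** SAP 5.3 counts TEAEs "up to the EOS/Safety Follow-up visit or 30 days after the last administration of evolocumab, whichever is earlier".
- **Measure.** 9.6.1 names none. SAP Table 9-1 lists both subject incidence and exposure-adjusted rate for adverse events.

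The SAP does not state that off-drug values enter the groups. That follows from the absence of any limit.

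**The concern.** Events stop counting 30 days after the last dose, but LDL-C values keep counting to EOS. A sample drawn long after an event can therefore decide the group in which that event is tabulated. If the event ended treatment, it also caused the later rise in LDL-C, so group membership is partly a consequence of the outcome.

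An 'all' rule has a second weakness: it is easier to satisfy with two samples than with eleven. Membership therefore also depends on how long a subject was followed.

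Protocol 2.3 gives the long-term effects of LDL-C below 40 mg/dL as part of the study's purpose, and 9.6.1 is the only SAP section that sets AEs against on-study LDL-C. A reader who takes 'all <40' against 'all ≥40' as a safety comparison by LDL-C level could be reassured or alarmed by an artefact.

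**Working it through.** **Plan's own figure.** None bears on this point. The only computed design figure, SAP Table 3-1, does reproduce: at 5%, 2 × 1.96 × √(0.05 × 0.95 / 5000) = 1.208%. It plays no further part.

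**Step 1: LDL-C after stopping.** Protocol 2.1 gives a reduction of about 55% to 75% against placebo. Off-drug value = on-drug value / (1 − reduction). It reaches 40 mg/dL when the on-drug value is 40 × (1 − 0.55) = 18, or 40 × (1 − 0.75) = 10. Most stoppers who are sampled will therefore have a value ≥40.

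**Step 2: where those subjects go.** One value ≥40 ends membership of 'all <25' and 'all <40' and confers 'any ≥40'. An earlier OLE value <40 bars entry to 'all ≥40'.

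This was simulated with 400,000 subjects per scenario. All inputs except the reduction are assumptions: an AE that always ends treatment, with 5-year risk 5.0% unrelated to LDL-C; on-drug median 25, 30 or 40 mg/dL; log SD 0.5 between and 0.25 within subjects; samples at weeks 12, 24, 48 to 216 and 260.

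- With all stoppers sampled, of those who would have been 'all <40' on continued treatment, 72-95% fall into no 'all' group, 2-27% stay, and 0.4-3.0% reach 'all ≥40'.
- The 5.0% risk then appears as 0.1-1.4% in 'all <40' and 6.7-10.5% in 'all ≥40'. With half of stoppers sampled it appears as 2.9-3.6% and 6.3-9.0%.

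This is the extreme case: an AE term that always ends treatment.

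**Step 3: SAEs, of which only some end treatment.** All inputs are assumptions: first-SAE rate 10 per 100 patient-years (PY), unrelated to LDL-C; 4%/year background stopping; 3%/year loss; LDL-C × 2.5 from 28 days after stopping; on-drug median 30 mg/dL; between-subject log SD 0.45; TEAE window to min(EOS, stop + 30 days). Ranges cover within-subject log SD 0.2 and 0.45 and repeat runs of the same model.

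| SAEs that end treatment | 2% | 5% | 10% | 25% |
|---|---|---|---|---|
| 'All <40' rate per 100 PY, complete off-drug sampling | 9.9 | 9.7 | 9.2-9.4 | 8.2-8.3 |
| Rate ratio 'all <40' / 'all ≥40', complete | 0.96-0.98 | 0.89-0.95 | 0.76-0.88 | 0.54-0.71 |
| Same, half of stoppers unsampled | 0.97-0.99 | 0.93-0.97 | 0.86-0.93 | 0.69-0.83 |
| Crude incidence ratio, complete | 1.17-1.39 | 1.13-1.32 | 1.07-1.19 | 0.90 |

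With no AE stopping the rate ratio is 1.00, but the crude ratio is already 1.19-1.46. At 10%, the other groups read: 'any <40' 9.9, '2 consecutive <40' 9.8-9.9, 'any ≥40' 10.2-10.5.

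**Step 4: why the two measures disagree.** Mean follow-up at risk = crude incidence / rate. At 10% stopping, complete sampling:

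- Within-subject SD 0.2: 'all <40' 0.343 / 0.0932 = 3.7 PY; 'all ≥40' 0.320 / 0.1060 = 3.0 PY. Rate ratio 9.32 / 10.60 = 0.88; crude ratio 34.3 / 32.0 = 1.07.
- Within-subject SD 0.45: 0.328 / 0.0935 = 3.5 PY; 0.275 / 0.1183 = 2.3 PY. Rate ratio 9.35 / 11.83 = 0.79; crude ratio 32.8 / 27.5 = 1.19.

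'All ≥40' has the shorter time at risk, which lowers its crude incidence.

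**Step 5: sensitivity.** A wider grid (median 25, 30 or 40; rebound × 2 or × 3; both within-subject SDs; between-subject SD 0.3 or 0.45) gave complete-sampling rate ratios of 0.52-0.96 at 5% and 0.38-0.91 at 10%. The lowest values arise where 'all ≥40' holds about 1% of subjects or fewer. With half of stoppers unsampled, the 'all <40' rate itself ran from 9.7 to 10.5 at 5% and 9.6 to 11.0 at 10%, so its direction is not fixed.

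**Step 6: alternatives under no true effect.**

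- On-treatment samples only: 'all <25' reads 10.3-11.4 at 10% and 10.7-13.3 at 25%, now too high, because early stoppers have few samples.
- Week-12 landmark: 9.98-10.01. Most recent prior LDL-C with matching person-time: 9.95-10.04. Both held in every base setting.

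**The case against.** **The effect is small where stopping is rare.** Entry requires that "Subject has completed FOURIER (Study 20110118) while still receiving assigned investigational product", and Protocol 4.1.2 excludes anyone for whom "Investigational product was permanently discontinued during FOURIER for any reason, including an adverse event or serious adverse event". Low AE stopping is therefore plausible. At 2-5%, 'all <40' reads 9.7-9.9 against a true 10. For all TEAEs (assumed 50 first events per 100 PY, 0.5-2% of them ending treatment) the 'all' rate ratio was 0.95-0.99. This stands.

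**The objective is largely served elsewhere.** The secondary objective concerns subjects achieving LDL-C <40 mg/dL. 'Any <40' and '2 consecutive <40' match that and are close to sound. AEs leading to withdrawal and reasons for stopping are reported separately (SAP 9.5.1, 9.2), and SAP 8.4 leaves room for bias sensitivity analyses. This also stands, though none of these provisions addresses the 'all' groups.

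**The added analysis dilutes a real effect.** This stands and is counted as a cost under the fix.

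A reader might infer three stronger things that the documents do not support:

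- *That AEs carry subjects from 'all <40' into 'all ≥40'.* An earlier low OLE value prevents it, and few subjects make that move.
- *That the low-LDL-C tables are biased toward safety whichever way they are read.* That holds for exposure-adjusted rates with off-drug samples taken as planned, but 9.6.1 names no measure and crude incidence can point the other way. Off-drug samples may also be missing, since Protocol 8.1 provides that "Subjects can decline to continue receiving evolocumab and/or other protocol-required therapies or procedures at any time during the study but continue participation".
- *That the whole section is unsound.* The distortion is mainly in the 'all' groups and in AEs that end treatment.

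**Conclusion.** The point holds in limited form. The 'all' groups use every OLE value, so a treatment-ending AE can take a subject out of 'all <25' and 'all <40', and membership also depends on length of follow-up. On exposure-adjusted rates with complete off-drug sampling, sustained low LDL-C then looks somewhat safer than it is: a ratio of about 0.9-0.95 at 5% AE stopping and 0.76-0.88 at 10%, when the truth is 1. Crude incidence gives about 1.2-1.4 from follow-up length alone.

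The artefact can also mask a real effect. If subjects with a long-term on-drug level <40 truly had 1.5 times the rate, the 'all' rate ratio would read 1.49 with no AE stopping, but 1.14-1.30 at 10% and 0.80-1.04 at 25%.

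These sizes rest on assumed event rates, stopping, LDL-C distribution and rebound, none of which the documents fix. The tables are descriptive, so the harm is a misread table, not a wrong test.

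**What to change.** Keep the existing tables and make these changes to SAP 9.6.1:

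1. Add one supportive analysis in which LDL-C class is fixed before the event. It could be a week-12 on-treatment landmark that counts later TEAEs, or the most recent prior on-treatment LDL-C (<25, 25 to <40, ≥40 mg/dL) with matching person-time. Report exposure-adjusted rates; SAP 5.1 already defines the end of TEAE follow-up.
2. State which measure the existing tables use.
3. Add a note that the 'all' groups are not comparisons by LDL-C level.

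Limiting the 'all' groups to on-treatment samples is not a substitute (step 6 of the working).

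Cost: SAP wording and moderate programming, with no new data. Downsides:

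- Events before the first usable sample drop out (6.7% of first SAEs in the simulation, if that sample is week 12).
- In the time-updated version, LDL-C values can be about 24 weeks old, and up to about 44 weeks old between weeks 216 and 260 (260 − 216 = 44).
- A true effect is diluted: an assumed 1.5 reads about 1.2-1.3, against about 1.3-1.5 for the existing 'all' rate contrast at 5% AE stopping or less. That is a reason to show both.
- The landmark describes early level and the time-updated version current level, so neither fully captures delayed or cumulative effects.
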